The second analysis aims to evaluate the treatment effect in the principal stratum of patients that tolerate and fully adhere to DHFCL. This analysis is performed in two steps. In the first step, data from patients randomised to the intervention group are used to construct a propensity score (PS) model for discontinuation due to intolerability of the DHFCL. In the second step, the analysis as described in section 6.1 is performed with weights based on the propensity scores. The propensity score will be constructed with logistic regression with intolerability (yes/no) as outcome variable in the intervention groups only. The model will include patient characteristics and

variables related to diabetes status measured at baseline. Patient characteristics include age, sex, educational level. Diabetes-related variables include TIR, duration of diabetes and patient reported daily insulin use. Variables to be included in the PS model may be subject to change based on available numbers (e.g. the number of discontinuing patients and valid observations for baseline variables) and clinical information on reasons for discontinuation. Outcomes and other variables measured during follow-up will not be included in the PS model.

The PS model will be used to estimate predicted probabilities of discontinuation due to intolerability for patients in the control group, these probabilities will be used as weights. Weights will only be applied in the control group. In the intervention group only two weights will be applied: a weight of 0 for patients who discontinued due to intolerability (i.e. effectively excluding these patients from the analysis) and a weight of 1 for all others. The weight will be applied for the analysis as described in section $6.1.^{28}$

8. Safety analyses

All safety outcomes will be presented for all events from baseline to final visit. Analyses will have a similar approach as with the secondary endpoints in the case of sufficient numbers of events.

9. Planned interim analyses

A formal interim analysis for primary and secondary outcomes is not planned. A Data Safety Monitoring Board will be established to monitor (S)AEs.

10. Subgroup analyses

In exploratory analyses, the primary and key secondary outcomes will be assessed separately for interaction with certain baseline variables as described below.

Subgroup analyses will assess the effectiveness of the DHFCL by the following patient characteristics:

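### The principal-stratum sensitivity analysis weights controls by the probability of not tolerating DHFCL, which is the reverse of the stratum it sets out to describe

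*SAP*

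**What the plan says.** The second analysis in SAP section 7.3.2 states its target: "The second analysis aims to evaluate the treatment effect in the principal stratum of patients that tolerate and fully adhere to DHFCL". It has two steps.

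- **Model.** Data from the DHFCL groups are used to build a "propensity score (PS) model for discontinuation due to intolerability of the DHFCL". It is a "logistic regression with intolerability (yes/no) as outcome variable in the intervention groups only". On covariates the SAP says: "Patient characteristics include age, sex, educational level", and "Diabetes-related variables include TIR, duration of diabetes and patient reported daily insulin use".
- **Weights.** In the DHFCL group there are two values: "a weight of 0 for patients who discontinued due to intolerability" and "a weight of 1 for all others". In the control group the model supplies "predicted probabilities of discontinuation due to intolerability for patients in the control group, these probabilities will be used as weights".

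The weighted data then go through the section 6.1 analysis. That section has two models. The first contains time, treatment and their interaction. The second adds baseline TIR, age and sex.

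Nowhere does the SAP take the complement of the predicted probability or recode the modelled event as tolerance.

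**The concern.** The two sides of the comparison are pointed at different patients. The 0/1 weights on the DHFCL side keep the tolerant patients. The control weights are largest for those whose baseline profile most resembles a patient who would stop for intolerability, and smallest for those who would very probably tolerate the device.

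What is at stake is one of the two analyses that section 7.3.2 adds because the ITT effect does not show the full potential of the device and the per-protocol analysis may be biased. A programmer who follows the text literally would get a plausible estimate labelled as the effect in tolerant patients, and nothing in the output would reveal the error. Turning the weight round after the results are known would be a departure from the plan.

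**Working it through.** The SAP gives no figure here to reproduce. The check is algebra, followed by illustrations of size.

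**1. What each weight targets.** Let f(x) be the baseline covariate distribution, equal in both groups by randomisation, and p(x) the probability of stopping DHFCL for intolerability.

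- DHFCL patients kept with weight 1: distribution proportional to f(x)·(1 − p(x)).
- Controls weighted as written: proportional to f(x)·p(x), the distribution of the intolerant patients.
- Controls weighted by 1 − p: proportional to f(x)·(1 − p(x)), the same as the DHFCL patients kept.

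This step needs no assumption about the data.

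**2. Two-stratum example.** From SAP section 3.1: control mean 78, effect 7. Assumed: two equal strata with control TIR 83 (low risk of intolerance) and 73 (high risk), and the stratum risks in the table.

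- High-risk share among tolerant DHFCL patients: (1 − p_high) / [(1 − p_high) + (1 − p_low)]
- High-risk share among controls weighted as written: p_high / (p_high + p_low)
- Estimate = 7 + 10 × (control share − DHFCL share)

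For risks 0.05 and 0.25 the shares are 0.75/1.70 = 0.441 and 0.25/0.30 = 0.833. The DHFCL mean is 0.559 × 90 + 0.441 × 80 = 85.59 and the weighted control mean is 0.167 × 83 + 0.833 × 73 = 74.67. The difference is 10.92.

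| p_low / p_high | DHFCL share | Control share as written | Estimate as written | Weight 1 − p | No weights |
|---|---|---|---|---|---|
| 0.05 / 0.15 | 0.472 | 0.750 | 9.78 | 7.00 | 7.28 |
| 0.05 / 0.25 | 0.441 | 0.833 | 10.92 | 7.00 | 7.59 |
| 0.05 / 0.35 | 0.406 | 0.875 | 11.69 | 7.00 | 7.94 |
| 0.10 / 0.30 | 0.4375 | 0.750 | 10.125 | 7.00 | 7.625 |

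The weight as written does worse than no weighting at all. Swapping the two TIR values reverses the sign of the error.

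**3. Continuous version with the arm 1 control values.** Control mean 78, SD 17 (section 3.1). Assumed: 7%, 10% or 20% intolerant; log-odds of intolerance falling by 0.5 or 1.0 per SD of baseline TIR; correlation r between baseline and 12-month TIR of 0.5 or 0.7. With baseline TIR in SD units,

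bias = 17 × r × (mean baseline TIR of tolerant − mean baseline TIR of intolerant).

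Numerical integration gives a mean gap of 0.481 to 0.927 SD. The smallest bias is 17 × 0.5 × 0.481 = 4.1 and the largest 17 × 0.7 × 0.927 = 11.0.

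- True control mean among tolerant patients: 78.3 to 80.1.
- Control mean with weight p: 67.7 to 74.7. With weight 1 − p: the true value.
- Error with no weights: 0.3 to 2.1 points.
- Effective control sample, (Σw)²/Σw²: 51-87% of n with p, 97-99.9% with 1 − p.

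**4. Simulation with an estimated model.** 85 per group; logistic model fitted in the DHFCL group on one covariate (intercept −2.0, about 12-16% intolerant); control TIR 5 points lower per SD of that covariate, residual SD 12; true effect 7; 3,000 replicates per setting.

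| Log-odds slope | Unadjusted, weight p | Unadjusted, weight 1 − p | Adjusted, weight p (SD) | Adjusted, weight 1 − p (SD) |
|---|---|---|---|---|
| 0 | 7.05 | 7.06 | 6.98 (2.00) | 6.99 (1.88) |
| 0.5 | 9.41 | 6.98 | 7.03 (2.16) | 7.03 (1.91) |
| 1.0 | 11.33 | 6.96 | 6.98 (2.42) | 7.02 (1.90) |

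The SD is that of the estimate across replicates. With weight p the effective control sample averages about 68 of 85 at slope 0.5 and 52 at slope 1.0. With 1 − p it is about 83 to 85.

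**The case against.** The literal sentence has no defence, but its consequences can be disputed on three grounds.

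**Adjustment.** The bias in steps 2 to 4 runs through a single covariate. The second section 6.1 model includes baseline TIR, and once that is in the model the bias in these illustrations disappears entirely. This stands, and the range of 4.1 to 11.0 belongs to the unadjusted model only. It does not rescue the plan. The first section 6.1 model has no baseline covariates, and education, diabetes duration and daily insulin use enter the propensity model but not the outcome model. If one of these, independent of the adjusted covariates, has an assumed correlation of 0.2 to 0.3 with 12-month TIR and the same link to intolerance as in step 3, the remaining bias is 17 × 0.2 × 0.481 = 1.6 to 17 × 0.3 × 0.927 = 4.7 points. Precision is lost in either case.

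**Inputs.** The rate of intolerability and its relation to TIR are assumed, and so is the direction of that relation. With no relation there is no bias. This also stands: the direction of the weight is certain, the size is not.

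**Importance.** This is a supportive analysis. Section 7.3.2 calls the ITT effect the one of primary interest, and section 6.1 restricts p-values to the primary ITT analysis. That limits the consequence. It does not make the weight right.

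**Conclusion.** The concern holds. As written, the analysis compares DHFCL patients who tolerate the device with controls weighted to resemble those who do not, so in general it cannot estimate the effect it names. The direction of the error follows from the SAP's own definitions.

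Its size depends on data not yet seen. Without covariate adjustment, and under the stated assumptions, it is 4.1 to 11.0 TIR points against a planned effect of 7 in arm 1, with the control sample worth 51-87% of its nominal size. It is an overstatement if patients prone to intolerance have lower TIR and an understatement if they have higher TIR. A correctly specified adjustment removes the part due to baseline TIR, age and sex, and no more.

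The complement weight recovers the true value in these calculations because the modelled covariate carries the whole link between intolerance and control outcome. In the trial that remains an assumption. The primary ITT estimate, its test and the sample size are not affected.

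**What to change.** In the paragraph of SAP section 7.3.2 that sets the weights, state that each control patient's weight is 1 minus the predicted probability of discontinuation due to intolerability. Modelling tolerance as the outcome and using its predicted probability is equivalent. Leave the DHFCL weights of 0 and 1 as they are.

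The cost is one sentence in the SAP, with no effect on data collection or trial conduct. It should be made before the analysis is run.
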